7.3 Follow-up of AEs and ADEs

All reported AEs and ADEs should be followed until resolution or until the subject's participation in the study ends. Resolutions of such events are to be documented on the appropriate CRF pages. All AEs and ADEs that result in permanent discontinuation from this clinical trial, whether serious or not, will also be reported on the Subject Non-Completion of Study Form.

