5.1.2 Exclusion Criteria

Subjects will be excluded from the study if they *meet any* of the following Exclusion Criteria:

1.	Participation in a clinical trial of a drug or another device in the target area within 3
	months of study participation, or during the study.
2.	Any type of prior cosmetic treatment to the target area within 12 months of study
	participation e.g., radiofrequency, cryolipolysis, deoxycholate injection, or light-based
	treatments
3.	Prior injection of botulinum toxin, collagen, hyaluronic acid filler, or other dermal filler,
	and medium-depth to deep chemical peels, to the treatment area within 6 months of
	study participation
4.	History of systemic steroid use within 3 months; history of topical steroid use in the
	target area within 2 months
5.	History of systemic retinoid (isotretinoin) and therapeutic dose of Vitamin A within 6
	months of study participation
6.	Has a pacemaker, internal defibrillator, implantable cardioverter-defibrillator, nerve
	stimulator implant, cochlear implant or any other electronically, magnetically or
	mechanically activated implant

7.	Has metal implant(s) within the body that are local to the treatment area, such as surgical clips, plates and screws (metal tooth fillings or crowns will not exclude subject participation), or has , artificial heart valves or artificial joints
8.	Clinically significant concurrent illness, such as diabetes mellitus, cardiovascular disease, peripheral vascular disease or pertinent neurological disorders that in the opinion of the Investigator will confound participation in the study
9.	Diagnosed or documented immune system disorders
10.	History of any disease or condition that could impair wound healing
11.	History of diseases stimulated by heat, such as recurrent herpes zoster in the treatment
	area, unless treatment is conducted following a prophylactic regimen
12.	History of keloid formation, hypertrophic scarring or abnormal/delayed wound healing
13.	Infection, dermatitis, rash or other skin abnormality in the target area
14.	Currently undergoing systemic chemotherapy or radiation treatment for cancer, or history of treatment in the target area within 3 months of study participation
15.	Anticipated or planned need for surgery or hospitalization during the duration of the study

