5.3 Subject Discontinuation Criteria

If possible, every subject should remain in the study until completion of the required follow-up period. However, participation in this study is completely voluntary and a subject can choose to withdraw from the study at any time. In addition, a subject can be discontinued for any of the following reasons: the Principal Investigator decides that continuing in the study would not be in the subject's best interest, a subject is noncompliant with the protocol, a subject has a serious reaction to the treatment, or the study is stopped. In addition, subjects may be discontinued from the study if s/he develops any of the exclusion criteria during the study period. A subject will be considered lost to follow-up only after three unsuccessful, documented attempts to contact the subject have been made. Withdrawn subjects will not be replaced.

Confidential and Proprietary

All potential AEs and ADEs will be evaluated and must be recorded in the subject's medical chart and in the study case report forms. AEs and ADEs will be monitored and tracked from the time of the first RF treatment.

At each contact with the subject, the Investigator will seek information on AEs by specific questioning and, as appropriate, by examination. AEs may be observed by the Investigator and/or clinical research staff, elicited from the subject and/or family member or volunteered by the subject. All observed and volunteered adverse signs and symptoms (both expected and unexpected), regardless of severity or frequency, will be recorded in the (medical chart and CRFs). Included in the description should be the nature of the sign or symptom, the date of onset, date of resolution (duration), the severity, whether the event was expected or unexpected (anticipated or unanticipated), the relationship to study treatment or other therapy, the action taken (if any), and the outcome.

All SAEs and UADEs must be reported according to Cutera and IRB requirements.

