9.4 Safety Analyses

Device-related and procedure-related adverse device effects (ADEs) and subjects who prematurely terminate from the study due to an adverse device effect, including the treatment-related pain ratings, will be tabulated and analyzed. For a given ADE term, counting will be done by subject, not by event, i.e. for a subject reporting the same ADE more than once, the event will be counted only once, at the most severe and longest duration. The number and percentage of subjects experiencing each ADE Term will be descriptively summarized. Subject pain ratings during treatment will also be summarized descriptively.

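### Follow-up of an unresolved adverse event stops when participation ends, so an event that leads to exit or is open at week 12 can lose its later course and final outcome

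*Combined protocol and SAP*

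**What the plan says.** - **Section 7.3** fixes when follow-up ends: "All reported AEs and ADEs should be followed until resolution or until the subject's participation in the study ends". The rule covers all events alike. Events that cause permanent discontinuation, "whether serious or not, will also be reported on the Subject Non-Completion of Study Form".
- **Section 5.3** opens with an aim: "If possible, every subject should remain in the study until completion of the required follow-up period". It then lists grounds on which a subject can be discontinued, among them that "a subject has a serious reaction to the treatment, or the study is stopped". It adds that "subjects may be discontinued from the study if s/he develops any of the exclusion criteria during the study period".
- **Section 5.1.2, criterion 13**, is one of those exclusion criteria: "Infection, dermatitis, rash or other skin abnormality in the target area".
- **The text on recording adverse events**, which follows 5.3 directly in the public version, asks for onset, resolution, severity, action taken and outcome of each event. It also states: "All SAEs and UADEs must be reported according to Cutera and IRB requirements".
- **Section 4.3.2.1** grades device effects as mild, moderate or severe after treatment and at every later visit.
- **Section 9.4** counts subjects for each effect term. If a subject reports the same effect more than once, "the event will be counted only once, at the most severe and longest duration". Section 9.2 rules out imputation for safety endpoints.

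**The concern.** Safety is one of the two objectives of this uncontrolled pivotal study, and the safety endpoint is the incidence and severity of adverse events. An event serious enough to end a subject's participation is the one whose course a reader of the safety section most wants to know: whether it worsened, how long it lasted, and whether it left a lasting effect. Under 7.3 as written, the exit that such an event may trigger is also the point at which the duty to follow it ends. An effect still present at the 12-week visit meets the same cut-off. The information at risk is tied to the severity and persistence of the event, so it would not be missing at random.

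**Working it through.** The plan states no figure on this point, so the check is a comparison of sections.

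**Step 1. Can an event lead to exit from the study, and not only from treatment?** Yes. Section 5.3 permits discontinuation for a serious reaction, and its sentence on exclusion criteria speaks of leaving the study. The public text does not distinguish stopping treatment from stopping observation. Section 7.3 itself foresees adverse events that result in permanent discontinuation from the trial.

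**Step 2. Does exit end follow-up of that event?** By 7.3, yes. Its two end points are resolution and end of participation. It names no third rule and refers to no other section.

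**Step 3. What is kept and what can be lost?**

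| Situation | Kept | Can be lost |
|---|---|---|
| Serious reaction, subject discontinued (5.3) | Occurrence, severity to date, status at exit, entry on the non-completion form, count in 9.4 | Later worsening, later course, final outcome |
| Skin abnormality in the target area, subject discontinued under criterion 13 (a literal reading) | Same | Same |
| Event still open at the 12-week visit | Occurrence, severity to date, status at that visit, count in 9.4 if device- or procedure-related | Same |

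**Step 4. Does the analysis section deal with open events?** Not in the text shown. Section 9.4 has a rule for combining repeat reports but none for events without a resolution date. With no imputation under 9.2, nothing in the analysis marks an event whose duration was cut off by exit.

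**Step 5. Do the other provisions close the gap?** They narrow it. The aim of keeping subjects in the study sets no duty once a subject has been discontinued. The non-completion form records the event at exit and does not extend observation. The sentence on SAEs and UADEs governs reporting to the sponsor and IRB. It sets no follow-up period in the protocol and does not reach non-serious, anticipated effects.

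**Scale.** Section 9.1 plans to enrol 39 subjects, so one subject is 1/39 = 2.6% of enrolment. This describes the size of the study only. It does not measure the loss, because the documents give no expected rate of discontinuation for adverse events or of events open at week 12.

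**The case against.** The strongest reply is that the planned safety results are largely protected. The endpoint is incidence and severity. An event that ends participation has already been recorded, is entered on the non-completion form, and is counted in 9.4, which also tabulates subjects who leave because of a device effect. This stands: incidence is not affected, and the gap is limited to later severity, course and final outcome.

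Two further objections also stand. Both discontinuation grounds are permissive, and 5.3 begins by asking that subjects stay. In addition, much of sections 6 and 7 is not public, so an early-exit visit or an SAE follow-up rule may exist there, and the sponsor and IRB requirements for serious events cannot be seen. Against this, 7.3 is visible and states its own end point without pointing to any such rule.

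A reader might infer more than the text supports, in four ways:

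- *That reported durations will be biased short.* The longest-duration wording in 9.4 is a rule for collapsing repeat reports, and the public text plans no summary of durations. The truncation affects the record of the individual event, not a visible planned analysis.
- *That an open event would have no recorded outcome at all.* The recording text asks for an outcome for every event, so status at exit should be on file. What may be missing is the final outcome.
- *That local skin reactions will routinely remove subjects through criterion 13.* Nothing says a reaction to treatment is to be handled as that criterion, and grading effects at every later visit presupposes that affected subjects stay.
- *That the loss can be expressed as a confidence bound on an event rate or as a number of follow-up days.* A bound for events that were never seen says nothing about the course of an event that was seen and counted. The days lost depend on when the exit occurs.

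**Conclusion.** The concern holds in a limited form. Read together, 5.3 and 7.3 allow the end of participation to be also the end of observation for an unresolved event, and the events most exposed are serious reactions and persistent effects. The consequence is an incomplete record of later severity, course and final outcome for a few subjects. It does not undermine the incidence table or the study as a whole. The number of subjects affected cannot be estimated from the documents.

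The conclusion rests on two assumptions: that the visible 7.3 is the operative follow-up rule, and that no unpublished part of sections 6 or 7 overrides it. If such a rule exists, a cross-reference in 7.3 would answer most of the point. The change is worth making because it is cheap and concerns a stated objective of the study.

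**What to change.** 1. **Section 7.3.** For device- or procedure-related events and SAEs that are unresolved at discontinuation or at the last visit, record status and outcome until the event resolves or is judged stable, unless the subject withdraws consent to contact. If a rule of this kind already stands elsewhere in the protocol, refer to it here.
2. **Section 9.4.** List events unresolved at last contact separately, and do not treat their duration as complete.
3. **Sections 5.3 and 7.3.** Reconcile the two so that it is clear that discontinuation does not end safety follow-up of an open event. This concerns observation only; the grounds for discontinuation remain for the sponsor and investigators to set.

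The cost is a wording amendment with IRB approval, occasional contact with the few subjects who have an open event, and a slightly later final safety record for them. Sample size, treatment and the efficacy analysis are unchanged.

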8 POTENTIAL RISKS / BENEFITS

Table 04 Potential Study Risks

8.2 Potential Benefits

The subjects may or may not benefit from the treatment. Potential benefits include improved appearance of the wrinkles and sagging skin treated in the face or submental region. There is no guarantee of success.

8.3 Risk Management

The Investigator chosen for this study will have extensive and safe experience with the use of RF systems in dermatology applications. This is the most critical element in managing subject risk. In addition, the Investigators will be trained on the use of the Cutera RF device and any investigational handpieces.

9 DATA ANALYSIS PLAN

9.1 Sample Size

The primary objective is to

is statistically greater than 50%.

Under the assumption that the true population response rate is 76%, 35 subjects will provide 80% power to reject the primary hypothesis. To allow for up to a 10% dropout rate, 39 subjects will be enrolled. The planned sample size of up to 35 subjects was determined based on clinical judgment to provide sufficient information to evaluate safety and efficacy of RF treatment for wrinkle reduction in the face and/or submentum region.

9.2 Analysis Sets

The efficacy analysis set will include all enrolled subjects who complete one RF treatment session using the study device.

The safety analysis set will include all subjects enrolled in the study who start the RF treatment session using the study device.

Missing data will not be imputed for efficacy or safety endpoints.

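### Efficacy set requires a completed session and missing outcomes are not imputed, so tolerability failures can leave the denominator and the response rate can be inflated

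*Combined protocol and SAP*

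**What the plan says.** Section 9.2 (Analysis Sets) uses two entry rules. The efficacy set is "all enrolled subjects who complete one RF treatment session" with the study device; the safety set is "all subjects enrolled in the study who start the RF treatment session". The same section adds: "Missing data will not be imputed for efficacy or safety endpoints".

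Other sections bear on this:

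- Section 4.3.1.5 gives two treatments in total, so the efficacy set asks for only one of the two.
- Section 5.3 allows discontinuation if "a subject has a serious reaction to the treatment", among other reasons, and does not replace withdrawn subjects.
- Section 9.1 tests a rate against 50%, assumes a true rate of 76%, and plans 35 subjects for 80% power and 39 enrolled to cover up to 10% dropout.
- The efficacy endpoint visible in sections 4.1.1 and 9.3 is the investigator's rating 12 weeks after the final treatment.
- Section 9.4 tabulates early terminations due to an adverse device effect, together with pain ratings.

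No visible text counts a subject without a rating as a non-responder, and none plans a sensitivity analysis for missing outcomes.

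**The concern.** Entry to the efficacy set depends on something that happens after treatment begins. There are two separate ways out of the response-rate denominator:

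1. **Set definition.** A subject who starts a session, stops it and never completes one counts for safety but not for efficacy.
2. **No imputation.** A subject who completes one session and then leaves stays in the efficacy set by definition, but has no 12-week value to analyse. This route covers all dropout, whatever the cause, and is probably the larger one.

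There is no control arm that would lose subjects in the same way. If the lost subjects are less likely to be responders, their absence raises the observed rate directly and makes it easier to exceed 50%. A subject who could not tolerate the treatment is more plausibly a failure than a success, so for that group the likely direction favours the device.

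**Working it through.** **Inputs.** From section 9.1: null rate 0.50, assumed rate 0.76, 35 evaluable, 39 enrolled, 10% dropout. Alpha and sidedness are not visible, so I use one-sided 0.05, 0.025 and 0.01 as an assumed range. The number lost, k = 0 to 4 of 39, is also assumed; its upper end is the planned dropout (39 − 35 = 4). All tests are exact binomial.

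**Step 1: the plan's own figures.** Enrolment: 35 / (1 − 0.10) = 38.9, rounded up to 39, which agrees. Power at n = 35 with a true rate of 0.76:

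| One-sided alpha | Reject at | Exact alpha | Power |
|---|---|---|---|
| 0.05 | ≥23/35 | 0.0448 | 94.3% |
| 0.025 | ≥24/35 | 0.0205 | 88.8% |
| 0.01 | ≥25/35 | 0.0083 | 80.0% |

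The stated 80% is matched only at about 0.01. That level is inferred, not stated.

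**Step 2: size of the gap.** Suppose 39 start, k are lost, all k are non-responders, and the rest respond at 76%. The all-starters rate is then 0.76 × (39 − k)/39.

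| k lost | All-starters rate | Observed-case excess (points) |
|---|---|---|
| 0 | 76.0% | 0 |
| 1 | 0.76 × 38/39 = 74.1% | 1.9 |
| 2 | 0.76 × 37/39 = 72.1% | 3.9 |
| 3 | 0.76 × 36/39 = 70.2% | 5.8 |
| 4 | 0.76 × 35/39 = 68.2% | 7.8 |

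**Step 3: can the conclusion change?** One-sided p = P(X ≥ r | n, 0.5), adding lost subjects to the denominator as failures:

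| Responders | n = 35 | n = 36 | n = 37 | n = 39 |
|---|---|---|---|---|
| 24 (borderline at 0.025) | 0.020 | 0.033 | 0.049 | 0.100 |
| 27 (77%, near the planned 76%) | 0.0009 | 0.002 | 0.004 | 0.012 |

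At 0.025, one added failure reverses 24/35. At 0.05, 24 responders still pass with two added failures but not with four. At 0.01, 24/35 already fails; the borderline result there is 25/35 (p = 0.008), and 25/39 gives p = 0.054. A result of 27 responders survives four added failures at 0.05 and 0.025, but not at 0.01.

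**Step 4: false success in the worst case.** Let the true rate among all 39 starters be 50%, with four lost, all non-responders. The rate among the 35 observed is 0.50 × 39/35 = 55.7%. Then P(X ≥ 24 | 35, 0.557) = 8.5% at nominal 0.025, against 2.0% without selective loss. With one lost, it is 2.5% against 1.7%.

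**Step 5: power if every missing value counts as failure.** At one-sided 0.025, 27/39 is needed. With none lost, power is 87.9%; with four lost, it is P(X ≥ 27 | 35, 0.76) = 53.0%. At 0.01, 28/39 is needed, and the figures are 79.2% and 37.3%.

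**The case against.** A reader might infer that the response rate is inflated, and that the direction of bias is known. The documents do not support that. Inflation needs at least one such loss, and a lower response rate in those lost than in the rest. No rate of aborted sessions is given. For dropout unrelated to tolerability, the direction is uncertain.

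A reader might also take the efficacy set to mean 12-week completers. It does not: completing one of two sessions is enough to enter it, and later losses arise from the no-imputation rule. Nor does a serious reaction imply a missing rating. Section 5.3 permits discontinuation in that case but does not require it, and asks that subjects stay in the study where possible.

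Three further points deserve weight:

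- **Hidden text.** The primary objective in section 9.1 is largely blank. So is section 9.3.1, which the table of contents lists as the primary endpoint analysis. The endpoint tested against 50%, its timing and its responder definition are not visible, and a handling rule could sit there. If it does, it would need reconciling with the general no-imputation sentence in section 9.2.
- **Edge case.** 24/35 is the smallest passing result at one-sided 0.025. A result near the planned effect is much more robust.
- **Partial visibility.** Section 9.4 would show readers how many subjects stopped for an adverse device effect, although it does not carry them into the response rate.

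All three stand as limits on the size of the problem. None removes the mismatch in section 9.2 or supplies a visible sensitivity analysis.

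**Conclusion.** The point holds in conditional form. As written, section 9.2 lets subjects who fail on tolerability leave the efficacy denominator by two routes, and in an uncontrolled test against 50% this can inflate the response rate. The excess runs from zero, with no losses, to 7.8 points if all four planned dropouts are non-responders; a single tolerability failure accounts for 1.9 points. A borderline success can reverse, while one near the planned effect would usually stand.

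This rests on four assumptions: 76% response among those observed, every lost subject a non-responder, an exact one-sided binomial test at an alpha that is not visible, and a tested endpoint that shares the 12-week timing of the visible one. It is a worthwhile correction to a stated rule, not evidence that the result will be biased.

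**What to change.** In section 9.2:

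1. Define the efficacy set as all subjects who start the first RF treatment, in line with the safety set.
2. Count as non-responders those who stop because of discomfort or an adverse device effect and have no 12-week rating. Where a rating exists, use it.
3. Keep the observed-case result.
4. Pre-specify a sensitivity analysis that counts every missing 12-week value as non-response.

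If the text not shown already contains a handling rule, align it with section 9.2 instead.

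The cost is a few sentences and one extra analysis, with no new visits or data. The reported rate may be slightly less favourable, and some power is lost if such losses occur. The all-missing-as-failure analysis has only about 53% power at one-sided 0.025 with 4 of 39 lost, so it belongs as a sensitivity analysis and not as the primary one.

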9.3 Analysis of Efficacy Endpoints

9.3.1

9.3.2

Endpoint Analyses

efficacy endpoints will be analyzed descriptively.

 Principal Investigator's assessment of improvement at 12 weeks post-final treatment (Physician's Global Assessment)

9.4 Safety Analyses

Device-related and procedure-related adverse device effects (ADEs) and subjects who prematurely terminate from the study due to an adverse device effect, including the treatment-related pain ratings, will be tabulated and analyzed. For a given ADE term, counting will be done by subject, not by event, i.e. for a subject reporting the same ADE more than once, the event will be counted only once, at the most severe and longest duration. The number and percentage of subjects experiencing each ADE Term will be descriptively summarized. Subject pain ratings during treatment will also be summarized descriptively.

